9.1. Subject Populations for Analysis

Intent-to-Treat (ITT) Population: All randomized subjects who take at least 1 dose of study drug. The ITT Population will be used in all efficacy analysis and subjects will be analyzed according to their randomized treatment.

Per Protocol (PP) Population: All subjects in the ITT population who have no major protocol deviations that affect the validity of the efficacy measurements. The PP Population will be used for sensitivity analysis of the efficacy endpoint. The criteria for inclusion in the PP Analysis Set will be finalized prior to study unblinding and detailed in the SAP.

Safety Population: All randomized subjects who receive at least 1 dose of study drug, with subjects grouped according to the treatment they actually receive. The Safety Population will be used in all safety analyses.

PK Population: All randomized subjects who take at least 1 dose of study drug. This analysis set comprises all subjects included in the Safety Population who did not violate the protocol in a way that might affect the evaluation of the effect of the study drug(s) on the PK assessment (ie, without major protocol violations or deviations).

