9.3.3.2. Analysis of Secondary Endpoints

The key secondary endpoint (change from baseline in caudate volume as assessed via vMRI at Month 12) will be analyzed by a mixed model repeated measures (MMRM) model using all available vMRI data up to the Month 12 Visit. The model will include fixed effects for treatment, baseline vMRI, and disease stage (by PIN_{HD} bin for Stage 2 only and by TFC for Mild Stage 3 only). The intercept and time of collection will be included as a random effect nested within subjects. The unstructured covariance matrix will be used in the model. The rate of changes will be compared between treatments and the least squares (LS) mean differences at Month 12 will also be provided.

For change from baseline in cUHDRS, a MMRM analysis (repeat at visit) will be performed using all data collected up to 12 months. The model will use treatment group, visits (categorical), treatment by-visit interaction, disease stage as fixed factors, CAG, age, and CAG by age interaction as covariates. The LS mean estimates for the change from Month 12, the difference between pairwise comparison with placebo, confidence intervals, and 2-sided p value will be presented. A similar model will be used for UHDRS sub-scores and PBA-s. Rate of changes in these scores will also be explored.

For by disease stage analyses, PIN_{HD} category (0.180 to 0.679, 0.680 to 1.520, or 1.521 to 4.930) will be used as a fixed factor for Stage 2 only, and TFC score (11, 12, or 13) will be used as a fixed factor for Mild Stage 3 only.

A repeated measure analysis model, similar to the analysis model used for blood tHTT protein, will be used for blood and CSF mHTT protein. Dose-response relationships will be explored and a by-visit summary of blood tHTT and blood and CSF mHTT protein will be displayed.

An analysis of covariance model with dose and Baseline in the model will be used to analyze change from Baseline to Month 12 in mHTT protein (in blood and CSF). Nominal p values and 95% confidence interval for each pairwise comparison will be calculated.

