2. SUBJECT POPULATIONS FOR ANALYSIS

2.1. Intent-to-Treat (ITT) Population

The ITT population will include all randomized subjects who take at least one dose of the study drug. This ITT Population will be utilized for all efficacy analyses, with subjects analyzed according to their assigned randomized treatment.

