Blood tHTT protein	Stage 2 and Mild Stage 3 HD subjects aged 25 years and older as defined by the protocol I/E criteria (ITT Population)	Change from baseline in blood tHTT protein at Month 12	Discontinuation of study treatment (due to any reason); data after the last dose of study drug + 30 days will be excluded.	Same as primary analysis for primary efficacy endpoint	Analysis of secondary endpoint
CSF mHTT protein	Stage 2 and Mild Stage 3 HD subjects aged 25 years and older as defined by the protocol I/E criteria; outliers will be excluded (ITT Population excluding outliers)	Change from baseline in CSF mHTT protein at Month 12	Discontinuation of study treatment (due to any reason); data after the last dose of study drug + 30 days will be excluded.	Same as primary analysis for primary efficacy endpoint	Analysis of secondary endpoint
CSF mHTT protein	Stage 2 and Mild Stage 3 HD subjects aged 25 years and older as defined by the protocol I/E criteria (ITT Population)	Change from baseline in CSF mHTT protein at Month 12	Discontinuation of study treatment (due to any reason); data after the last dose of study drug + 30 days will be excluded.	Same as primary analysis for primary efficacy endpoint	Sensitivity analysis of secondary endpoint
Blood mHTT protein	Stage 2 and Mild Stage 3 HD subjects aged 25 years and older as defined by the protocol I/E criteria (ITT Population)	Change from baseline in blood mHTT protein at Month 12	Discontinuation of study treatment (due to any reason); data after the last dose of study drug + 30 days will be excluded.	Same as primary analysis for primary efficacy endpoint	Analysis of secondary endpoint

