The change from baseline at Month 12 will be analyzed using the same model as the primary analysis. The LS means from the model will be back-transformed to present model-based percent change in geometric means from baseline for each treatment group. The treatment effect (calculated as the difference in model-based percent

change in geometric means from baseline between PTC518 and placebo groups) at Visit 8 (Month 12) along with their 95% CIs, and the normal p-values (2-sided) for each pairwise comparison (PTC518 5 mg vs. placebo/ PTC518 10 mg vs. placebo) will be provided. The delta method will be applied to estimate the treatment differences and standard errors.

- Change from baseline in CSF mHTT protein at Month 12

The CSF samples for mHTT protein will be collected pre-dose at Visit 2 (baseline) and subsequent post-baseline visits. The samples will be analyzed by the same bioanalytic laboratory as blood tHTT protein. For the same reason as blood tHTT protein, a sample may have multiple results. For the analysis purpose, a single result at baseline and at each post-baseline visit will be derived according to the following steps:

1. The change and percent change from baseline will be calculated for each post-baseline visit using the baseline result from same run.
2. If the baseline result is $\leq 2 \times$ the lower limit of quantification ($\leq 3.44 \text{ pg/mL}$), the entire run will not be used for the analysis.
3. For each subject, the result from the last run will be used for the analysis for both baseline and post-baseline visits.

An MMRM, similar to the analysis model used for blood tHTT protein, will be used to analyze this endpoint. The LS means from the model will be back-transformed to present model-based percent change in geometric means from baseline for each treatment group. The treatment effect (calculated as the difference in model-based percent change in geometric means from baseline between PTC518 and placebo groups) at Visit 8 (Month 12) along with their 95% CIs, and the normal p-values (2-sided) for each pairwise comparison (PTC518 5 mg vs. placebo/ PTC518 10 mg vs. placebo) will be provided. The delta method will be applied to estimate the treatment differences and standard errors.

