CSF mHTT levels are generally very low in patients with HD ([Wild 2015, Rodrigues 2020](#)). In this study, an ultra-sensitive single molecule counting (SMC) immunoassay on the SMCxPRO platform is utilized to measure mHTT levels in CSF. It has been observed in the interim analysis that the majority of samples were $< 3 \times$ the limit of reliable quantification. To address the inherent variability in quantifying protein production at the low level of assay detection, notable outliers will be excluded from the analysis. The notable outliers are defined as follows: if the difference in the percent change from baseline in CSF mHTT levels between Month 12 and the average of Months 6 and 9 exceeds (increases or decreases) 40%, the subject will be excluded from the analysis, because it is highly unlikely to observe such a substantial shift in mHTT levels over a short period of time, especially months after achieving steady state exposure.

In addition, a sensitivity analysis will be performed with outliers included.

- Change from baseline in blood mHTT protein at Month 12

An analysis identical to that performed for blood tHTT at Month 12 will be conducted.

For each secondary PD endpoint, the post-baseline values and percent changes from baseline will be summarized descriptively by treatment group for each visit.

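### The lead CSF mHTT analysis at Month 12 drops subjects because of their own Month 12 result, and the full ITT analysis is only a sensitivity analysis

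*SAP*

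**What the plan says.** - **The rule (SAP 5.3, CSF mHTT).** Take the Month 12 percent change from baseline and the mean of the Month 6 and Month 9 percent changes. If the difference "exceeds (increases or decreases) 40%, the subject will be excluded from the analysis". The reason given is assay variability at low concentrations, and that the values are not credible "because it is highly unlikely to observe such a substantial shift in mHTT levels over a short period of time".
- **Its status (SAP 3.1, Table 1).** The row labelled as the analysis of this secondary endpoint has the population "outliers will be excluded (ITT Population excluding outliers"). The ITT row is labelled as sensitivity. Section 5.3 agrees: "In addition, a sensitivity analysis will be performed with outliers included".
- **The general population rule.** Protocol 9.1: "The ITT Population will be used in all efficacy analysis". SAP 2.1: "This ITT Population will be utilized for all efficacy analyses". SAP Section 5 repeats this for efficacy and PD endpoints.
- **The protocol's model.** Protocol 9.3.3.2 says a repeated-measures model like that for blood tHTT "will be used for blood and CSF mHTT protein", and adds an analysis of covariance for Month 12. Neither has an outlier rule.
- **Declared changes.** SAP 3.5 states that there are none.
- **An existing assay filter (SAP 5.3, CSF step 2).** If the baseline result is at or below 3.44 pg/mL, "the entire run will not be used for the analysis". This uses the baseline value only.

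**The concern.** Month 12 is the endpoint, and the Month 12 value always enters the exclusion test. The retained set is therefore chosen partly on the outcome, after randomisation and after treatment. An aberrant Month 6 or Month 9 value can also remove a subject whose Month 12 value is sound.

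The justification is circular. A large late shift is set aside because lowering is presumed stable by then, but durability to Month 12 is what this endpoint should show. If lowering were lost late, the subjects who show the loss are the ones most likely to be removed.

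The rule is also incomplete. It does not say outright whether 40% is percentage points or a relative change, or what happens when Month 6 or Month 9 is missing.

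The rule first appears in SAP version 1.0 (17 March 2025). That is after the June 2023 interim analysis and its June 2024 update at 12 months, and Section 5.3 cites interim assay levels as motivation. SAP 3.3 gives real safeguards: an independent team did the unblinded work, only summary results reached the sponsor's study team, and the cited observation concerns assay level, not a difference between arms.

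**Working it through.** **1. Text.** The protocol leaves detail to the SAP (Protocol Section 9), so absence of the rule from the protocol is not in itself an error. Replacing the analysis population for a secondary endpoint is more than detail. It contradicts Protocol 9.1, SAP 2.1 and SAP 5, and SAP 3.5 does not declare it. This part needs no arithmetic.

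**2. Inputs for size.** The plan gives no SD, power or expected exclusion rate for CSF mHTT, so there is no figure to reproduce. Assumptions: independent log-normal error with log-SD s at baseline and Months 6, 9 and 12; percentage-point cut; 1,000,000 simulated subjects per arm. A subject is excluded if |pc12 - (pc6 + pc9)/2| > 40. Effect = difference between arms in percent change of geometric means. The baseline filter and a quantification floor are not modelled.

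**3. Stable 40% lowering.** With proportional error, an active subject's percent changes vary 0.60 times as much as a placebo subject's. The 40-point cut thus acts like 40/0.60 = 66.7 points on the placebo scale, and more placebo subjects are removed.

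| s | Excluded, placebo | Excluded, active | Estimate (true -40) |
|---|---|---|---|
| 0.10 | 0.2% | 0.0% | -40.0 |
| 0.15 | 4.0% | 0.2% | -39.3 |
| 0.20 | 12.0% | 1.8% | -38.1 |
| 0.25 | 21.0% | 5.5% | -36.8 |
| 0.30 | 29.2% | 10.8% | -35.3 |

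The imbalance disappears with additive error (SD 20% of baseline: 12.1% v 12.0%) or a relative cut (s = 0.20: 10.0% v 10.0%).

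**4. Lowering that wanes by Month 12 (s = 0.10 to 0.25).**

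| Months 6 and 9 to Month 12 | True Month 12 effect | Estimate under the rule |
|---|---|---|
| 40% to 30% | -30.0 | -30.0 to -29.3 |
| 20% to 10% | -10.0 | -10.1 to -11.9 |
| 30% to 15% | -15.0 | -15.3 to -17.6 |
| 40% to 20% | -20.0 | -20.5 to -23.5 |
| 40% to 0% | 0.0 | -9.0 to -15.8 |

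In the last row the expected shift is 0 - (-40) = 40 points, equal to the cut, so about half of the active arm (47 to 49%) is removed. Additive error with SD 10 to 20% of baseline gives -8.4 to -15.1, so this does not depend on proportional error.

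**5. Loss in some subjects only.** Suppose active lowering is 45% and one subject in five truly loses it by Month 12. The true active change is exp(0.8 x ln 0.55) - 1 = -38.0%. The rule removes about 54 to 66% of those who lost the effect, and the retained active arm shows about -43 to -44%. The retained placebo mean also drifts down as s grows, so the between-arm estimate runs from -42.9 (s = 0.10) to -39.4 (s = 0.25) against a true -38.0.

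**6. Rejection of a true Month 12 null.** The 144 subjects at 2:1 give 144 x 1/3 = 48 placebo and 144 x 2/3 / 2 = 48 per dose. Month 12 log change was regressed on arm and log baseline, with s = 0.20, an assumed between-subject log-SD of 0.4, and 5,000 trials per setting. With full loss after 20%, 30% or 40% earlier lowering, the null is rejected in 17%, 40% and 75% of trials, against 5% with all subjects. In one stage (24 v 24) it is 23% and 41% after 30% and 40%. With no effect at any visit the rule keeps about 4 to 5%.

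**7. Precision.** At s = 0.20 and stable 40% lowering, the retained SD is 0.925 (placebo) and 0.974 (active) of the full SD, and the retained fractions are 0.880 and 0.982. The standard error ratio, rule to all subjects, is sqrt((0.925²/0.880 + 0.974²/0.982)/2) = 0.98.

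**The case against.** **Assay noise is real, and the rule can buy precision.** SAP 5.3 reports that most samples lay below three times the limit of reliable quantification. If 2 to 10% of samples carry a gross extra error (assumed log-SD 0.7 to 1.0, on s = 0.10 to 0.20), the rule's standard error is 0.77 to 0.95 of the all-subject one. The ITT standard error is then about 5% (1/0.95 = 1.05) to 30% (1/0.77 = 1.30) larger. Under stable 40% lowering the rule's estimate stays conservative, at -40.0 to -36.6. The baseline filter cannot catch an aberrant post-baseline value. This stands as a reason to keep the rule as a supporting analysis.

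**The large biases need an extreme case.** The highest rejection rates need the whole active arm to lose its effect on treatment between Month 9 and Month 12. Nothing in the documents suggests that, and data beyond 30 days after the last dose are already excluded. Milder waning gives small bias. Fewer subjects may also contribute CSF: at an illustrative 30 v 30, the three rejection rates fall to 12%, 25% and 52%. This stands, and it limits the weight of steps 4 and 6.

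**Little formal inference is at risk.** The p-value is nominal, without multiplicity control. The rule is symmetric and the same in every arm. Both analyses are prespecified, and by-visit summaries are planned. The interim work was descriptive and covered about 36 Stage 2 subjects. All true, but the selected result remains the designated one.

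**The wording is clearer than alleged.** A difference between percent changes reads most naturally as percentage points, and a missing Month 12 cannot trigger the rule. Largely fair. The handling of a missing Month 6 or Month 9 remains open.

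**Conclusion.** The concern holds and should be fixed. The lead CSF mHTT estimate is not a comparison of all randomised and treated subjects, it conflicts with the ITT rule in both documents, and SAP 3.5 does not declare the departure. These points rest on the text alone.

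The size of the bias cannot be fixed from the documents. Under the assumptions above, the rule is neutral to conservative if lowering is stable and makes almost no difference if 40% wanes to 30%. It favours the drug increasingly as more of the effect is lost, up to an apparent 9 to 16 point lowering where there is none. The sign of the bias thus depends on the durability that the endpoint is meant to measure. The prespecified all-subject analysis limits the harm, as does the endpoint's non-key, nominal status.

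**What to change.** 1. In SAP Table 1 and Section 5.3, make the ITT MMRM on log CSF mHTT the analysis of the secondary endpoint, keeping the baseline filter in step 2.
2. Keep the 40% exclusion as the sensitivity analysis. State its scale (percentage points, or relative/log) and how a missing Month 6, 9 or 12 is handled.
3. Report the number excluded by arm and by direction (rise or fall).
4. List the rule in Section 3.5.

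The cost is SAP text and two Table 1 rows, with no new data and no new analysis, because both analyses are already planned. The statistical price is a wider confidence interval if gross outliers occur. Under plain log-normal error (40% lowering, s = 0.15 to 0.30) the standard error differs by less than 2% either way.

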5.4. Exploratory Endpoints Analysis

The exploratory endpoints that will be analyzed include:

- Change from Baseline in CSF mHTT protein at Month 3
- Change from Baseline in blood mHTT protein at Month 3
- Change from Baseline in whole brain, putamen, ventricular volume, and striatum (as assessed by vMRI) at Month 12
- Change from Baseline in UHDRS TFC sub-score at Month 12
- Change from Baseline in other UHDRS sub-scores including TMS, SDMT, and IS at Month 12
- Change from Baseline in 11 symptom domains in the short form of the PBA-s at Month 12
- Change from Baseline in the Functional Rating Scale (FuRST) at Month 12
- Change over time in blood *HTT* mRNA
- Change over time in plasma and CSF NfL
- [REDACTED]
- Change from Baseline in wearable accelerometer assessment TUG, 2-minute walk distance, and postural sway at Month 12

These endpoints will be summarized descriptively by treatment group for each visit. The relationship between biomarker endpoints and clinical endpoints will be explored by an association analysis.

5.5. Pharmacokinetic Endpoints Analysis

Descriptive summaries for plasma concentrations at pre-dose and post-dose and for CSF concentrations at pre-dose will be provided for each visit on PK Population. The accumulation ratio of the study drug will be calculated and summarized for both plasma and CSF concentrations. For plasma, the accumulation ratios will be calculated using the C_{trough} (plasma trough concentrations, also known as pre-dose concentrations) at Visits 3 (Month 1) through 8 (Month 12) as the numerator, with the pre-dose concentration at Visit 3 serving as the denominator for all visits. For CSF, the accumulation ratio will be calculated using the pre-dose concentrations at Visits 5 (Month 3) through 8 (Month 12) as the numerator, with the pre-dose concentration at Visit 5 serving as the denominator. Also, the CSF to plasma C_{trough} concentration ratio at each visit will be summarized descriptively.

5.6. Subgroup Analysis

To examine the uniformity of treatment effect in the subgroups, the primary and secondary endpoints will be summarized descriptively for the following subgroups:

- Disease stage (PIN_{HD} score class [0.180-0.679, 0.680-1.520, and 1.521-4.930] for Stage 2 only and by TFC score [11, 12, 13] for Mild Stage 3)

6. SAFETY ANALYSES

The safety analysis will be performed on the Safety Population.

6.1. Adverse Events

All AEs will be coded using the MedDRA Version 25.0. All AEs will be assigned a severity grade using Common Terminology Criteria for Adverse Events (CTCAE) Version 5.0 (refer to the study manual).

A treatment-emergent adverse event (TEAE) will be defined as an AE with onset date, or date of worsening if occurring prior to the first dose of study drug, between the date of first dose of study drug and the date of last dose of study drug + 30 days, inclusive. Only those TEAEs will be included in summary tables.

All AEs, treatment-emergent or otherwise, will be presented in subject data listings. An overview table of TEAEs, including number of subjects with TEAEs, treatment-emergent serious adverse events (TESAEs), TEAEs leading to discontinuation from study treatment, deaths, TEAEs by maximum severity, and treatment-related TEAEs, will be summarized by treatment group. A treatment-related AE will be defined as an AE with a relationship of possibly, probably, or related to the study treatment, as determined by the investigator.

In the summary tables, subjects may be counted under multiple SOCs and PTs, but for each SOC and PT, subjects are only counted once. If a subject has the multiple TEAEs in the same SOC or PT, the highest severity (5=fatal, 4=life-threatening, 3=severe, 2=moderate, 1=mild) recorded for the event will be presented and the closest drug relationship (1='Unrelated', 2='Unlikely to be Related', 3='Possibly Related', 4='Probably Related'), reclassified into Related ('Possibly Related', 'Probably Related') or Not Related ('Unrelated', 'Unlikely to be Related'), will be presented on the respective tables.

The following summaries will be produced for the TEAEs and TESAEs by treatment groups:

- TEAEs by SOC and PT
- TEAEs by PT (for cases where the incidence $\geq 5\%$ in either the 5 mg or 10 mg dose group)
- Treatment-related TEAEs by SOC and PT
- TEAEs by maximum severity
- TEAEs by relationship to study treatment
- TESAEs by SOC and PT
- Treatment-related TESAEs by SOC and PT
- TEAEs leading to discontinuation from study treatment by SOC and PT
- Treatment-related TEAEs leading to discontinuation from study treatment by SOC and PT

For the AE data the following rules will apply:

- For the derivation of treatment-emergent status (applicable to all AEs): If the start date/time of an AE is incomplete or missing, an AE will be assumed to be a TEAE,

unless the incomplete start date/time or the end date/time indicates an AE started before dosing.

- For the derivation of treatment-related status (applicable to TEAEs only): If the study treatment relationship for a TEAE is missing, a TEAE will be assumed to be a treatment-related TEAE.
- For the calculation of TEAE summary statistics: If the severity of a TEAE is missing, that TEAE will be counted under the 'missing' category.

All AEs, deaths, SAEs and TEAEs leading to discontinuation from study treatment will be presented in by-subject data listings.

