Once assigned treatment, subjects will take their assigned dose of study medication once a day. Subjects will be asked to return to the clinic every month after randomization until Visit 5 (Month 3) and then quarterly until Visit 8 (Month 12) or receive home care services in lieu of in-person visits (Section 3.6) to undergo study assessments. On Month 12, subjects will take their final dose of study medication and complete the end of study (EOS) assessments. Upon completion of Visit 8 (Month 12), subjects will have the option to enroll in Study PTC518-CNS-004-HD, a Phase 2 long-term extension study, to receive PTC518.

[figure not shown]
For subjects not enrolling in Study PTC518-CNS-004-HD, Visit 8 will be considered the End of Treatment visit, and there will be a Follow-Up Safety Visit on Month 13 via telephone/telehealth to collect adverse events (AEs) and an additional Follow-Up Safety Visit on Month 16 (ie, approximately 4 months after the last dose of study drug) to collect AEs [REDACTED]

[REDACTED]. A final Follow-Up Safety Visit will occur on Month 18 via telephone/telehealth to collect adverse event data.

The safety profile will be characterized via the assessment of treatment-emergent adverse events (TEAEs) and serious TEAEs, laboratory abnormalities, neurofilament light chain (NFL) levels in plasma and cerebrospinal fluid (CSF), and vital signs, the Columbia Suicide Severity Rating Scale (C-SSRS), electrocardiogram (ECG), [REDACTED], and physical examination.

[figure not shown]
The primary efficacy assessment includes blood collection for tHTT protein at Month 3. Secondary efficacy assessments include volumetric magnetic resonance imaging (vMRI) for change in caudate volume (key secondary); other secondary efficacy assessments include blood and CSF collection for mHTT protein at Month 12, and cUHDRS scores. Exploratory assessments will include blood and CSF collection for mHTT protein at Month 3, clinical scales (UHDRS sub-scores [with the exception of the behavioral examination], PBA-s [substituting for the behavioral examination], and Functional Rating Scale [FuRST] 2.0); assessment of gait, balance, and postural sway via Opal wearable devices; plasma and CSF NFL; [REDACTED]; and blood *HTT* mRNA. A complete Schedule of Assessments can be found in [Table 4](#) and the study design is pictured in [Figure 1](#).

Figure 1: Study Design

Abbreviations: ET, Early Termination

Figure 2: Randomization Schema

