3.5. End of Study Definition

The study will end when the last subject has completed the final assessment.

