8. ASSESSMENT OF SAFETY

8.1. Safety Parameters

The following have been defined as parameters regarding safety and tolerability:

- Abnormalities in vital signs
- Abnormalities in ECG parameters
- Abnormalities in clinical laboratory tests
- NfL levels in plasma and CSF
- Changes in C-SSRS scores
- TEAEs up to EOS
- TEAEs leading to premature discontinuation of study drug
- Treatment-emergent serious adverse events (SAEs) up to EOS
- Abnormalities in physical examination

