8.2.2. Definition of Serious Adverse Events

An SAE is an untoward medical occurrence or effect at any dose, regardless of whether it is considered to be related to the study intervention, which results in one of the following:

- Results in death. This includes all deaths on treatment or within 6 months after last study intervention administration, including deaths due to disease progression. Any death occurring later than 6 months following the last dose need not be reported as an SAE unless it is a result of an event that started within the period covered by the on-study definition. The reported AE should be the event that caused the death.
In addition, any AE resulting in death that occurs post the AE reporting period and that the investigator assesses as possibly related to the study intervention should also be reported as serious.

- Is life-threatening. This refers to an event in which the subject was at risk of death at the time of the event. It does not include an event that, had it occurred in a more severe form, hypothetically might have caused death.
- Requires hospitalization or prolongation of existing hospitalization (excluding hospitalizations for administration of the study intervention, procedures required by the study protocol, or treatment-related diagnostic procedures; other planned hospitalizations; or hospitalizations related only to progression of disease). Emergency room visits that do not require admission to the hospital do not fall into this category, but the event may still be serious due to another seriousness criterion.
- Results in persistent or significant disability or incapacity or substantial disruption of the ability to conduct normal life functions.
- Any other medically important event that the investigator or PTC judges to be serious or which is defined as serious by the regulatory agency in the local country. These are AEs that might not be immediately life-threatening or result in death or hospitalization but might jeopardize the subject or might require intervention to prevent one of the other outcomes listed above. Medical judgment should be exercised in deciding whether an AE is serious based on the above definition. Examples of such events are intensive treatment in an emergency room or at home for allergic bronchospasm, blood dyscrasias or convulsions that do not result in hospitalization, or development of drug dependency or drug abuse.

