8.2.4. Time Period and Frequency for Collecting/Reporting Adverse Event Information

The AE (both serious and nonserious) collection and AE reporting period begins with the signing of the ICF and continues until 6 months after the last dose of study medication. All AEs during this time period must be recorded whether or not the event is considered drug related.

For subjects who are screen failures, the active collection period for AEs ends when screen failure status is determined. Any SAEs occurring during screening procedures should be reported, and the appropriate causality assessment (ie, “not related” to study intervention) section of the SAE Report Form must be completed.

If the subject withdraws from the study and also withdraws consent for the collection of future information, the active collection period for AEs ends when consent is withdrawn.

Investigators are not obligated to actively seek information on AEs or SAEs after conclusion of the study participation. However, if the investigator learns of any SAE, including a death, at any time after a subject has been discharged from the study, and he/she considers the event to be reasonably related to the study intervention, the investigator must promptly notify PTC Pharmacovigilance Department via the SAE Report Form.

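### SAEs, fatal ones included, that begin more than 30 days after the last dose are collected for 6 months but have no planned count by arm

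*SAP*

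**What the plan says.** **Collection.** Protocol 8.2.4 starts AE collection at consent, and collection "continues until 6 months after the last dose of study medication". Protocol 8.2.2 sets the same reach for fatal events: "This includes all deaths on treatment or within 6 months after last study intervention administration, including deaths due to disease progression". Under Protocol 4.4, a subject who stops drug is still expected to be evaluated on the original visit schedule. Table 4 adds safety contacts at Months 13, 16 and 18.

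**Planned safety parameters.** Protocol 8.1 names "TEAEs up to EOS" and "Treatment-emergent serious adverse events (SAEs) up to EOS". It gives no treatment-emergent window in days. Protocol 9.3.2 plans to tabulate TEAEs. Protocol 9.3.2.1 plans AE frequencies by treatment group, with seriousness among the classifications, and does not limit them to TEAEs. The same subsection says that SAEs and AEs leading to death will be listed.

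**Tabulation.** SAP 6.1 sets the window by date of onset or worsening, "between the date of first dose of study drug and the date of last dose of study drug + 30 days, inclusive", and adds: "Only those TEAEs will be included in summary tables". The count of deaths is one item of the TEAE overview table. All AEs, SAEs and deaths also go to by-subject listings. SAP 3.5 declares no change from the protocol's planned analysis.

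**The concern.** The collection period and the tabulation window differ by about five months, and no table covers the difference. An SAE that begins on day 31 or later after the last dose is recorded and reported to the sponsor, but no planned output sets its frequency in one arm against another.

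That matters for two reasons. Comparing safety with placebo is a primary objective (Protocol 2.1). Listings also do not give a comparison by themselves: about 24 subjects per active arm and 36 on placebo are planned in each disease stage, so a reader would have to count events by hand and find the denominators. Stopping for a drug-related AE is one of the protocol's reasons for discontinuation (Protocol 4.4). The window may therefore close early more often in one arm than in another, and it does so during the randomized 12 months as well as afterwards.

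**Working it through.** The plan states no figure to reproduce. The check is window arithmetic.

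**Inputs**
- Month length of 30 days, as in SAP Table 2, where the Month 12 target is Day 360.
- Tables close at last dose + 30 days (SAP 6.1).
- AE collection closes at last dose + 6 months (Protocol 8.2.4), taken as 180 days.

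**Share of post-dose collection outside the tables**

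180 − 30 = 150 days, and 150 / 180 = 83%. With 6 months taken as 183 days, the gap is 153 days, or 84%.

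**Where the gap falls, by day of last dose**

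| Last dose | Tables close | Collection closes | Onset days in listings only | Of these, by Day 360 |
|---|---|---|---|---|
| Day 90 | Day 120 | Day 270 | 121–270 (150 days) | 150 |
| Day 180 | Day 210 | Day 360 | 211–360 (150 days) | 150 |
| Day 270 | Day 300 | Day 450 | 301–450 (150 days) | 60 |
| Day 360 | Day 390 | Day 540 | 391–540 (150 days) | 0 |

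For a completer, the Month 13 contact falls 30 days after the last dose, just inside the window. The Month 16 and Month 18 contacts fall at 120 and 180 days. Any event first reported there with onset after day 30 is listed only.

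**Which SAP text causes the gap**

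SAP 1 assigns assessments up to 30 days after Visit 8 to the double-blind period and says those data are analysed and reported in the CSR. An SAE at Day 200 in a subject who stopped at Day 90 belongs to that period. It is the TEAE definition in SAP 6.1 that keeps it out of the tables. SAP 1 sends to listings only what lies beyond the double-blind period.

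**Illustrative size**

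The documents give no late SAE rate, discontinuation rate or rollover rate. Assume a late SAE rate r per subject-year and follow every subject for the full 150 days. The expected number is n × r × 150 / 365, with n = 48 per dose (24 × 2 stages) and n = 72 on placebo (36 × 2 stages).

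| Assumed r | Per dose, n = 48 | Placebo, n = 72 |
|---|---|---|
| 0.02 | 0.39 | 0.59 |
| 0.05 | 0.99 | 1.48 |
| 0.10 | 1.97 | 2.96 |

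For the rate assumed, these counts are too high, because subjects who enter the extension leave this follow-up early.

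**The case against.** The best defence is that a collection period need not equal a tabulation window. A last dose + 30 days rule keeps the main tables close to drug exposure. The protocol sets no TEAE window, so the SAP is entitled to supply one. Nothing is hidden, because every AE, SAE and death is listed, and for SAEs and fatal AEs Protocol 9.3.2.1 itself mentions listings. After Month 12 many subjects may move to open treatment with PTC518, so the remaining follow-up is self-selected and unequal. All of this stands. It supports keeping the 30-day tables and making any later table supplementary. It does not supply a by-arm count of later SAEs, and Protocol 9.3.2.1 also planned AE frequencies by arm and seriousness.

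A reader might infer four stronger points that the documents do not support.

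- **That the SAP contradicts the protocol's EOS limit outright.** Protocol 1.2 puts EOS at Month 12: "On Month 12, subjects will take their final dose of study medication and complete the end of study (EOS) assessments". On that reading, the SAP window runs 30 days past EOS for a completer. Protocol 3.5 suggests a later point: "The study will end when the last subject has completed the final assessment". The term is ambiguous, and that is what needs repair.
- **That a stop at Day 90 loses 240 days.** 360 − 120 = 240 counts to Month 12, but required AE collection ends at about Day 270. The span affected is about 150 days.
- **That every death after day 30 drops out of the deaths row.** The cut-off is on onset. A late death from an event that began inside the window can count as a grade 5 TEAE. AEs with missing or incomplete start dates are treated as TEAEs unless the available dates show a start before dosing.
- **That SAP 1 removes early stoppers' events.** As shown above, SAP 6.1 does that.

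**Conclusion.** The point holds in a limited form. SAEs and fatal events with onset more than 30 days after the last dose are collected for 6 months and planned for listings only. The gap is about 150 of 180 post-dose collection days for each subject followed to the end of collection. For subjects who stop drug at or before about Month 6 and stay on schedule, all of it lies within the 12-month period. For completers, all of it lies after Month 13. Separately, the SAP does not say whether the deaths row takes deaths from late-onset events, and EOS has two readings.

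The conclusion rests on 30-day months and on collection running its full course. It ends sooner if consent to further data collection is withdrawn, and this placebo comparison ends sooner if the subject enters the extension. The 83% is a share of days, not of events. At the assumed rates, the late SAEs number from under one to about three per group. At such counts a clear tabulation is useful, but a formal comparison would say little. Sample size, power and the efficacy analyses are not affected. This is a cheap improvement to the SAP.

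**What to change.** - Keep the 30-day TEAE tables as they are.
- Add to SAP 6.1 one separately labelled by-arm table of all SAEs and all deaths, from first dose to the end of protocol AE collection (6 months after last dose). Cut it at the first extension-study dose for subjects who roll over. Show the number of subjects and the person-time followed in each arm, so that unequal follow-up is visible.
- State in SAP 6.1 whether the overview deaths row counts every death in the collection period or only deaths from TEAEs.
- Define EOS in Protocol 8.1 so that the safety parameters match the two windows.

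**Cost.** One extra table from data already collected, and two clarifying sentences. The table will include some off-drug events, and follow-up after Month 12 will be unequal between subjects, so it should be labelled supplementary. The part that uses Month 13 to 18 data can be produced only after the final database lock.
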